Sample size The planned sample size was based on data from a previous study, in which the uterine fibroids incidence was 1.278% per year in Asia and 3.745% per year in African-American women. Women over the age of 40 years were more likely to have uterine fibroids. A study also revealed that African-American females had lower level of serum 25-hydroxyvitamin D_3 as compared to Caucasian females. Vitamin D deficiency was shown to increase the risk of uterine fibroids in vitro, in vivo animal models and in clinical trials. We assumed an one-tailed α error of 0.05 and a power (1- β) of 0.8. If the rates were 3.745% for the control group and 1.278% for the intervention group, we propose to enroll 1160 participants (580 randomized to each arm) and allow for a dropout rate of 10% for an effective sample size of 1054.

Inclusion criteria

- 1. Volunteer to participate in the study with informed consent;
- 2. Females aged 35-50 who are confirmed with a normal, fibroid-free uterine structure, by means of transvaginal or abdominal ultrasonography;
- 3. Serum25-hydroxyvitamin $D_3 < 20 \text{ ng/ml}$, $\geq 12 \text{ng/ml}$.

Exclusion criteria

- 1.Use of sexual hormone, mifepristone, gonadotropin-releasing hormone agonist (GnRHa), or other medication which is likely to interfere with uterine fibroids within 3 months;
- 2. Pregnancy, lactation, postmenopause, or planned pregnancy within two years;
- 3. Allergic to vitamin D₃;
- 4. Suspected or identified as other tumors of genital tract;
- 5. History of hysterectomy or myomectomy;
- 6. History of osteoporosis or vitamin D deficiency taking vitamin D supplements within previous one month;
- 7. History of hyperparathyroidism, infectious diseases (tuberculosis, AIDS), autoimmune diseases, or digestive system diseases (malabsorption, crohn disease and dysentery);
- 8. Alanine aminotransferase (ALT) or aspartate transaminase (AST) more than 3 times of the normal upper limit, total bilirubin (TBIL) more than 2 times of the normal upper limit;
- 9. Creatinine levels $\geq 1.4 \text{ mg/dL}$ (123µmol/L) or creatinine clearance $\leq 50 \text{ ml/min}$;

- 10. History of malignant tumors;
- 11. Simultaneous participation in another clinical study with investigational medicinal product(s) or researcher thinks the subjects are not suitable for this trial.

Outcomes measures

The primary outcome is first diagnosis of uterine fibroids in different groups.

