The secondary outcomes include hypercalcemia, abnormal liver and renal function, and urinary calculus in different groups.

Withdrawal Subjects must be withdrawn from the study when one of the following criteria occurs:

- 1. At their own request. At any time during the study and without giving reasons, a subject may decline to participate further. The subject will not suffer any disadvantages as a result;
- 2. In the investigator's opinion, continuation of the study treatment would be harmful to the subject's health;
- 3. Obvious non-compliance;
- 4. Lost to follow-up;
- 5. Pregnancy;
- 6. Other medical or surgical treatments of uterine fibroids.
- 7. Receive other medical treatments which may affect the level of serum 25-hydroxyvitamin D₃ or other surgical treatments.
- 8. The level of serum calcium > 3.5 mmol/L or serum 25-hydroxyvitamin $D_3 > 100$ ng/mL.

Safety assessments Safety will be assessed by renal and liver function test, electrolyte, routine blood test, and serum 25-hydroxyvitamin D₃. Urine pregnancy test and serum 25-hydroxyvitamin D₃ level will be detected every three months. Other indicators are detected during the period of screening and after the treatment of every six months. Liver and urinary system ultrasound will be conducted after the treatment of 12 months and 24 months. The occurrence of any adverse events in trial participants will be recorded in the case report forms during each patient visit. We will withdraw patients who have severe adverse events, as it is unsafe for them to continue the trial. Meanwhile, we will give them relevant medical care and follow them up until the reaction has terminated.

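### The withdrawal rules take women out of the study rather than only off treatment, so fibroid scans stop for reasons that fall mainly on one arm

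*Combined protocol and SAP*

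**What the plan says.** The Withdrawal section opens with "Subjects must be withdrawn from the study when one of the following criteria occurs" and lists eight reasons. Criterion 2 applies when, in the investigator's view, "continuation of the study treatment would be harmful". Criterion 3 is "Obvious non-compliance", with no definition. Criterion 7 begins "Receive other medical treatments which may affect the level of serum 25-hydroxyvitamin" and also covers other surgery. Criterion 8 sets serum calcium and 25-hydroxyvitamin D limits.

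The Safety assessments section adds: "We will withdraw patients who have severe adverse events, as it is unsafe for them to continue the trial". The only later follow-up it states for these women is to "follow them up until the reaction has terminated".

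Under Outcomes measures, "The primary outcome is first diagnosis of uterine fibroids in different groups". Table 1 schedules gynecologic ultrasound at months 0, 6, 12, 18 and 24. Neither the text nor Table 1 extends these scans to withdrawn women, and neither gives an analysis set, a rule that women are analysed as randomised, a censoring rule or a missing-data rule. Figure 1, the flow diagram, was not available for this review.

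**The concern.** Read as written, a woman who meets one of these criteria leaves the study and her planned fibroid scans end. The scans provide the primary outcome, and a scan that was not done cannot be recovered in the analysis.

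The criteria do not bear equally on the two arms. Treatment is open-label and no product is stated for controls. Harm from study treatment, non-compliance with the product and the 25-hydroxyvitamin D limit therefore fall essentially on the intervention arm. For other criteria the balance is unclear: criterion 7 could arise in either arm, and criterion 3 might include missed visits in either arm.

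Removal thus depends on events after randomisation that differ by arm. If the women removed differ in fibroid risk from those who stay, part of the observed difference reflects who was removed. The direction cannot be known in advance. Few events are expected, so a modest distortion matters, most of all if the true effect is small or absent.

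**Working it through.** **Inputs from the plan (Sample size).** "If the rates were 3.745% for the control group and 1.278% for the intervention group"; one-sided α 0.05; power 0.80; 580 per arm; 10% dropout; effective total 1054. The source rates are annual.

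**The plan's own figure.** 1054 × 1.1 = 1159.4, which gives 1160. The plan names no formula. The pooled-z formula needs 497 per arm (994 in total), and 527 per arm gives 82% power. The point below does not depend on which formula was used.

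**Expected events at 580 per arm.**
- One year: 580 × 0.03745 = 21.7 and 580 × 0.01278 = 7.4.
- Two years, with risk 1 − (1 − p)²: 7.35% and 2.54%, or 42.6 and 14.7 events.

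**Selection with no true effect.** The documents give no removal fractions or risk ratios, so these are assumed. Both arms have 5% risk, about the midpoint of the two-year risks: (7.35 + 2.54)/2 = 4.9%. A fraction *w* of the intervention arm is removed, with *k* times the risk of the others. Each arm has 580 × 0.9 = 522 women.

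- Risk among those remaining: r = 0.05/(1 − w + wk).
- If removed women contribute half their follow-up: r[(1 − w) + 0.5wk]/[(1 − w) + 0.5w].
- Error: probability that a one-sided 0.05 pooled-z test declares benefit.

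Example, w = 0.10 and k = 2: r = 0.05/1.10 = 0.0455, so RR = 0.909. The null SE is √(2 × 0.0477 × 0.9523/522) = 0.0132, and the SE under the shifted risks is also 0.0132. Error = Φ[(0.00455 − 1.645 × 0.0132)/0.0132] = 9.7%.

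| w | k | RR among remaining | Error, no scans from removed women | Error, half follow-up |
|---|---|---|---|---|
| 5% | 2 | 0.95 | 7.1% | 6.0% |
| 10% | 2 | 0.91 | 9.7% | 6.9% |
| 10% | 3 | 0.83 | 15.8% | 8.9% |
| 10% | 0.5 | 1.05 | 3.3% | 4.1% |

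- With 10% removed from the intervention arm and 5% from controls, both at k = 2, the error is 7.0%.
- Equal selective removal in both arms gives 5.0%.
- Using 580 controls against 551 or 522 treated women gives 7.2%, 9.8%, 16.1% and 3.3% for the four rows with no scans.
- At a one-year risk of 2.5%, those rows become 6.4%, 8.0%, 11.6% and 3.8%.

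**How much would cancel the planned effect.** Suppose 58 of 580 per arm are lost and control losses carry the control rate. The removed intervention women would then need a one-year risk of (580 × 0.03745 − 522 × 0.01278)/58 = (21.72 − 6.67)/58 = 26%, about 20 times the planned 1.278%.

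**Cost of keeping these women (dilution).** Suppose a fraction *s* stops and reverts to control risk for the whole period. Intervention risk is then (1 − s) × 0.01278 + s × 0.03745.

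| s | Power, 580 per arm | Power, 522 per arm | n per arm for 80% | Two-year power, 580 per arm |
|---|---|---|---|---|
| 0 | 85% | 82% | 497 | 98% |
| 5% | 81% | 77% | 564 | 97% |
| 10% | 76% | 72% | 643 | 95% |
| 20% | 66% | 62% | 851 | 89% |

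**The case against.** The strongest reply is that the bias is probably small. The 10% allowance is for dropout of all kinds, and own request and loss to follow-up end scanning under any plan. No passage gives a reason why women removed for harm, non-compliance or laboratory limits should carry two or three times the fibroid risk. With 2% to 3% selectively removed at twice the risk, the same method gives an error of only 5.8% to 6.2%, or 5.4% to 5.6% with half their follow-up. A bias factor of 0.91 is minor beside the planned ratio of 0.34 (1.278/3.745). This stands as a limit on size. It does not remove the exposure, and it reassures least when the true effect is null or small.

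Second, Figure 1 might define who is analysed, and silence does not show that earlier scans would be discarded. That is fair, and the finding of absence covers the text and Table 1 only. A flow diagram is unlikely to undo the explicit withdrawal rule, and an analysis set cannot supply scans never taken.

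Third, the missing analysis rule is part of a wider gap, since the text has no analysis section. That is true. The part specific to the withdrawal rules is the loss of later scans, and analysis by randomised group needs those scans.

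Fourth, criterion 6 would normally follow a fibroid diagnosis, so little is lost there if earlier data are kept. This is accepted.

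**Conclusion.** The concern holds and should be fixed. As written, the plan ends outcome assessment on post-randomisation grounds that fall largely on one arm of an open-label trial. The size and direction of the bias cannot be derived from the documents. Under the assumptions shown, the one-sided error ranges from 3.3% to 15.8% with no scans from removed women, and from 4.1% to 8.9% if they contribute half their follow-up. It stays at 5.0% if selective removal is equal in both arms. These values rest on assumed removal fractions and risk ratios and are illustrations, not estimates. Moderate imbalance alone would not cancel or create an effect as large as the one planned. Confidence that the text works as described is high.

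**What to change.** Leave the criteria for stopping study treatment as they are, and separate stopping treatment from leaving the study.

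- Continue the six-monthly ultrasound already in Table 1 to month 24 for every randomised woman who can be contacted and has not withdrawn consent, where the investigator sees no safety reason against the scan. That judgement also covers pregnancy.
- Reconcile this with the Safety assessments sentence on severe adverse events, which treats continuing in the trial itself as unsafe.
- State that the primary comparison is by randomised group using all available scans. Exclude women meeting criteria 3 or 7 only in a sensitivity analysis.
- Add a missing-data sensitivity analysis for women who still leave.
- Restate the power with an allowance for women off treatment.

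The cost is an amendment to the withdrawal wording, an analysis statement and a revised power calculation. Scan cost is not documented. At most four scans per woman are involved, so if 10% of 1160 women stop (assumed), the ceiling is 116 × 4 = 464.

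The main downside is dilution. At the planned rates and 580 per arm, power falls to 76% if 10% stop, and 643 per arm would restore 80%. Full reversion to control risk for the whole period is close to the worst case. If the annual rates run for two years, power stays at 95%.
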